 - Definition of ER: proportion of patients with platelet count higher or equal than 30x10⁹/L and at least doble than baseline at first week (Day 7) from randomisation.
 - Definition of IR: proportion of patients with platelet count higher or equal than 30x10⁹/L in the first month (Day 30) from randomisation.
- To compare the difference of means between study arms of the maximum number of consecutive days with platelet response (CR, R, GR and TR) along the study period. We will evaluate them in the total sample and in the absence of any rescue treatment
- To compare the difference of means between study arms of the total number of days with platelet response (CR, R, GR and TR) along the study period. We will evaluate them in the total sample and in the absence of any rescue treatment.
- To evaluate and to compare the proportion of patients who need rescue treatments and proportion and time to treatment failures.
- To compare the time to loss of response (LoR) in patients who achieved response in both arms.
 - Definition of LoR: number of days from the first time the patient achieved a platelet count ≥30x10⁹/L until platelet count dropped below 30x10⁹/L measured on 2 occasions with more than 1 day apart or presence of bleeding
- To compare the difference between study arms in the proportion of patients requiring any rescue treatment along the study period.
- To compare the difference between study arms in the proportion of patients with adverse events (AEs), including serious adverse events (SAEs) and laboratory safety parameters. AEs will be graded according to National Cancer Institute Common Terminology Criteria for Adverse Events (CTCAE) version 5.0. Bleeding events will be carefully monitored.
- To compare the difference between study arms in the mean change in patients' bleeding from screening to Day 1, Week 8, Week 12, Moth 6, Moth 12andEnd of study Visit (visit 12 months after the last dose of study treatment) assessed with the ITP-bleeding tool in both arm.
- To compare the difference between study arms in the mean change in patients' quality of life from baseline Day 1 (the day of administration of the first dose of study medication) to Week 8, Month 6 (Day 180), Month12 (Day 365) from randomisation and End of study Visit (visit 12 months after

the last dose of study treatment) assessed with SF-36v2, FACIT-F and ITP-PAQ in both arms.

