- To evaluate the superiority of romiplostim plus dexamethasone vs dexamethasone alone after 12 months (≥365 days) from treatment cessation, if data available, in patients with newly primary immune thrombocytopenia in terms of sustained response off any ITP treatment (12mSROT-30 and 12mSROT-50) from treatment cessation and without WHO grade 2 or more bleeding.
- To evaluate the superiority of romiplostim plus dexamethasone vs dexamethasone alone in terms of complete response (CR), response (R) global response (GR) and response within the target range (TR) at 6 months (Day 180), at 12 months (Day 365) from randomisation and End of study Visit (visit 12 months after the last dose of study treatment). We will evaluate them in the who trial cohort but also in a subgroup that excludes patients receiving any rescue treatment. Or an additional sensitivity analysis will exclude patients receiving rescue treatment.
- To compare the time to first response defined as the time from randomization to first response (R) in both arms. We will evaluate this in the total sample and in the absence of any rescue treatment.
- To compare the proportion of patients with early response (ER) and initial response (IR) in both arms.
- To compare the duration of platelet response assessed as: the maximum number of consecutive days with platelet response (CR, R, GR and TR) and, the total number of days along the study period with platelet response (CR, R, GR and TR) in both arms. We will evaluate them in the total sample and in the absence of any rescue treatment.
- To compare the time to loss of response (LoR) in patients who achieved response in both arms.
- To compare the proportion of patients requiring any rescue treatment along the study period in both arms

- To evaluate and compare proportion of treatment failure and time to treatment failure.
- To evaluate the safety and tolerability of study treatments in both arms.
- To compare the difference between study arms in the mean change in patients' bleeding
- To compare the change in patients' quality of life from baseline Day 1(the day of administration of the first dose of study medication) to 2 (Week 8), Month 6 (Day 180), Month 12 (Day 365) and End of study Visit (visit 12 months after the last dose of study treatment) assessed with SF-36 v2, FACIT-F and ITP-PAQ in both arms.
- To describe and compare healthcare resources use (HRU) and loss of productivity in both study arms.

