In the DEX arm, dexamethasone will be administered 40 mg daily x 4 days for up to 3 cycles every 14 to 28 days.

The use of commercial dexamethasone will be authorized up to 3 days, in case the patient is attended in emergency care while the criteria for the study are being checked and labeled study medication is assigned.

c. Treatment duration and monitoring

The monitoring will be the same in both arms with slight differences to allow for dose adjustments of romiplostim:

In the ROM + DEX arm patients will be reviewed weekly for 8 weeks (56 days). After Week 8, patients will be reviewed every 2 weeks (14 days) for 8 additional weeks and then monthly until Week 52 (Month 12) from randomization.

- o If romiplostim dose should be modified, patients will be reviewed weekly until a stable dose of romiplostim is reached for at least 4 weeks (28 days). After that, patients will go on with visits every 2 weeks (14 days) for 8 weeks and then monthly until Week 52(Month 12) from randomization.
- In the DEX arm, patients will be reviewed weekly until the completion of dexamethasone cycles and for a minimum of 8 weeks (56 days). After that, every 2 weeks (14 days) for 8 additional weeks and then monthly until Week 52 (Month 12) from randomization.

Once romiplostim or dexamethasone is stopped or after 365 days since randomization, patients should be clinically evaluated minimum every 4+/- 1 week for 12 months and continuation of treatment should be decided on an individual basis by the treating physician.

If patient needs treatment again it will be prescribed according to routine clinical practice. In case romiplostim is used, it will not be supported by the sponsor.

d. Criteria for dose adjustments

Dose adjustments for romiplostim will be based on platelet count as described in previous Dosage and administration section.

No dose adjustment for dexamethasone is permitted.

e. Rescue medication

We will consider rescue medication IVIg, platelet transfusion or prednisone. Tranexamic acid will be not considered rescue medication. Rescue medication will be used as follow:

- In the ROM + DEX arm, if platelets counts are lower than 20x10⁹/L or bleeding symptoms related to thrombocytopenia are present between romiplostim doses, rescue therapy with IVIg(maximum dose 2 gr/kg in total during 1 to 5 days) can be used. Prednisolone is not allowed in this arm.

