- In the DEX arm, if platelet counts are lower than 20x10⁹/L or bleeding symptoms related to thrombocytopenia are present between cycles, rescue therapy with IVIg (maximum dose 2 gr/kg in total during 1 to 5 days) or low doses of prednisone (0,5 mg/kg/d) can be used. If patients use rescue treatment with prednisone, they should be decreased as soon as possible and stopped within 8 weeks.

f. Treatment failure

In the ROM + DEX arm, it would be considered treatment failure if platelets are lower than 30x10⁹/L after 4 weeks with romiplostim at 10 mcg/kg/week or rescue

medication is needed to get this level of platelets despite this dose of 10mcg/kg/week for 4 weeks.

In DEX arm, it would be considered treatment failure if platelets are lower than 30x10⁹/L after 3 cycles of dexamethasone or if rescue medication is needed to get this level of platelets despite the 3 cycles of dexamethasone.

In both arms, treatment failure will be considered to in those patients bleeding who are refractory to therapy in whom it is considered clinically in their best interests to escalate or switch treatment in a way that does not align with the protocol treatment schedules. Patients will be discussed with Steering Committee before to be considered treatment failure.

If patients lose response on the DEX arm, they can be switched from one arm to the other (to TPO-RA), but outside the trial. The treatment will be provided by their centre and this information will be collected up in the CRF. The patients will be considered a treatment failure.

g. Accountability

The study medication (i.e., romiplostim, dexamethasone) will be sent directly from the sponsor to the investigator's site pharmacy preceded by the Regulatory Green Light. The medication is to be used exclusively in the clinical trial according to the instructions of this study protocol.

When a drug shipment is received, the Investigator or designee will check the amount and condition of the delivery, drug expiration date, and sign the Receipt of Shipment Form provided. The Receipt of Shipment Form should be faxed or sent by e-mail to the CRO. The original form will preliminarily be retained at the site and will be collected at the next monitoring visit by the monitor and stored in the TMF at CRO. A copy will remain in the Investigator File at the site. In case of shipment problems, the Investigator or designee shall contact the CRA as soon as possible.

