An Investigational Product Accountability Log will be provided for the trial medication. The record must be continuously updated and contain the dates, quantities and compounds of drugs received, medication identification number(s), the patient identification number to whom the trial medication was dispensed, date and quantity of medication dispense and the initials of the dispenser.

h. Concomitant medication

Throughout the study, investigators may prescribe any concomitant medications or treatments deemed necessary to provide adequate supportive care, except for those listed in section *Prohibited drugs*.

For concomitant therapies therapy name, indication, dose, unit, frequency, route, start date and stop date will be recorded.

Reduction or discontinuation of permitted concurrent ITP therapies may begin once a subject's platelet count has increased to ≥50x10⁹/L.

Rescue medication will also be collected.

Concomitant therapies are to be collected from screening through the EOS visit, as applicable.

i. Prohibited drugs

The following medications are not permitted during this study. After treatment failure, they will be allowed:

- Other thrombopoietic receptor agonists
- Any cytotoxic agents, alkylating agents
- Rituximab
- rHuTPO
- Interferon
- Herbal supplements that are associated with bleeding side effects including, but not limited to, gingko biloba, garlic, ginseng, fish oil, dong quai, feverfew. Garlic and ginseng taken through a normal diet are not excluded.
- Aspirin at doses higher than 100mg or anticoagulant drugs.
- Treatments for ITP other than allowed rescue medications (includings plenectomy).
- Any other investigational agents that are not approved

Should a subject require administration of any of the medications listed above, sponsor should be consulted before the medication is administered, when possible. In all cases, sponsor must be informed within 24 hours. Sponsor may decide that the subjects will be ineligible to receive additional administrations of study medication.

STUDY SCHEDULE AND STUDY FLOW-CHART

Study flow-chart

[figure not shown]

Table 3. Schedule of study assessments.

DEX arm

Visit number	Visit 0 Screening	Visit 1 Baseline	Visit 2- 8	Visit 9	Visit 10, 11, 12, 13 and 15	Visit 17-18	Visit 19	Visit 20-24	Visit 25	Visit 26-36 (Periodical clinical evaluation after the end of study medication ¹¹)	Visit 37 (End of study Visit) ¹²	

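### Section 9.f makes loss of response followed by a switch to a TPO-RA a treatment failure in the DEX arm only, so on the 9.f/9.c reading the compared failure proportion favours ROM+DEX

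*Protocol*

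**What the plan says.** Section 9.f of the protocol defines treatment failure in four parts.

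- **ROM+DEX:** platelets below 30x10⁹/L after 4 weeks at 10 mcg/kg/week, or rescue needed to reach that level despite 4 weeks at that dose.
- **DEX:** platelets below 30x10⁹/L after 3 cycles, or rescue needed to reach that level despite them. No assessment date is given.
- **Both arms:** "In both arms, treatment failure will be considered to in those patients bleeding who are refractory to therapy", where a switch or escalation outside the protocol schedule is judged best. Cases go to the Steering Committee first.
- **DEX only:** "If patients lose response on the DEX arm, they can be switched from one arm to the other (to TPO-RA), but outside the trial". The consequence follows: "The patients will be considered a treatment failure". Neither bleeding nor refractoriness is required.

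Section 9.c covers what happens once study treatment has stopped, in both arms: "If patient needs treatment again it will be prescribed according to routine clinical practice". It foresees romiplostim among the options: "In case romiplostim is used, it will not be supported by the sponsor". It does not call such re-treatment a failure.

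Section 9.i lists drugs that are prohibited during the study and allowed only after treatment failure. The list includes other TPO-RAs and, more generally, ITP treatments other than the permitted rescue medication.

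Treatment failure is compared between arms. Section 5.c sets the objective "To evaluate and compare proportion of treatment failure and time to treatment failure", and section 1.j lists the outcome: "To evaluate and to compare the proportion of patients who need rescue treatments and proportion and time to treatment failures".

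**The concern.** Romiplostim is meant to be stopped, either at the end of a taper with platelets above 50x10⁹/L or at Day 365. Some patients in each arm will therefore lose response off study drug and be treated again, and a TPO-RA is an obvious choice in both. Under 9.f that event is a failure by rule in DEX. In ROM+DEX it is a failure only if the patient is also bleeding and refractory. A patient stopped at 1 mcg/kg every 14 days is nowhere near the 10 mcg/kg/week condition.

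An endpoint with an extra failure criterion in one arm can show a between-arm difference where the clinical courses are the same. Here the arm spared the criterion is the experimental one, in an open-label trial. Because the protocol itself assigns the failure status, this is a rule fixed badly and not a detail left for the SAP.

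**Working it through.** **1. The same event under each rule.** Take a patient who responds, completes study treatment as planned, loses response without bleeding, and is given a TPO-RA.

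| Rule | DEX | ROM+DEX |
|---|---|---|
| Arm-specific platelet or rescue rule | Possibly met: below 30 after 3 cycles, undated | Not met after a taper to 1 mcg/kg/14 days; reachable only in edge cases, such as a Day 365 stop on a high dose or commercial romiplostim later raised to the maximum |
| Both-arms rule (bleeding and refractory) | Not met | Not met |
| TPO-RA switch sentence | Failure | No such rule |

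Loss of response while romiplostim is still being given is different: Table 2 raises the dose up to 10 mcg/kg, so the ROM+DEX rule can be reached. The asymmetry concerns loss after a planned stop.

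**2. Illustration of size.** The protocol gives no figure for treatment failure, so there is none to reproduce. Inputs:

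- From section 5.b: high-dose dexamethasone is initially effective in 85%, and 50% relapse within 6 months.
- From section 11.b: 63 patients per arm, two-sided 5% level.
- Assumed: the 50% applies to responders; both arms have the same true course; the 15% who do not respond are failures in both arms; the undated 3-cycle rule does not itself catch relapse.
- Assumed: a share s of relapsers receives a TPO-RA, and a share c of the equivalent ROM+DEX events is nevertheless captured as failure. The protocol gives neither.

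Loss of response = 0.85 × 0.50 = 0.425. Recorded failure in DEX = 0.15 + 0.425 × s. Recorded failure in ROM+DEX = 0.15 + 0.425 × s × c. The gap is 0.425 × s × (1 − c), while the true difference is zero. The last three columns give recorded ROM+DEX failure and, in brackets, the chance of p<0.05 in favour of ROM+DEX (uncorrected chi-square test, exact binomial enumeration).

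| s | DEX | ROM+DEX, c = 0 | c = 25% | c = 50% |
|---|---|---|---|---|
| 10% | 19.3% | 15.0% (9%) | 16.1% (6%) | 17.1% (5%) |
| 25% | 25.6% | 15.0% (31%) | 17.7% (19%) | 20.3% (10%) |
| 50% | 36.3% | 15.0% (79%) | 20.3% (52%) | 25.6% (25%) |
| 75% | 46.9% | 15.0% (98%) | 23.0% (82%) | 30.9% (47%) |

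The gap runs from 0.425 × 0.10 × 0.50 = 2.1 percentage points to 0.425 × 0.75 × 1 = 31.9 points. When every equivalent event counts in both arms (c = 1), the chance is 2.4 to 2.9%, as it should be.

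**3. Off-drug observation time.** The last dexamethasone dose falls between Day 4 (one cycle) and Day 60 (three cycles 28 days apart, starting on Days 1, 29 and 57). The fastest uninterrupted romiplostim taper from 3 mcg/kg is:

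- 3 mcg/kg on Days 1, 8, 15 and 22
- 2 mcg/kg on Day 29
- 1 mcg/kg on Days 36, 43, 50 and 57
- 1 mcg/kg every 14 days on Days 71, 85, 99 and 113

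The last romiplostim dose therefore falls between Day 113 and Day 365. Table 3 ends at Month 18 in DEX and Month 24 in ROM+DEX. Removing the DEX-only sentence is not enough by itself: an open-ended common rule would still count off-drug events over unequal periods. A fixed window fits both schedules. Twelve months after the latest planned dose is Day 60 + 365 = Day 425 in DEX, before Month 18, and Day 365 + 365 = Day 730 in ROM+DEX, which is Month 24.

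**The case against.** The strongest objection is section 9.i. Its prohibition covers ITP treatments other than permitted rescue, in both arms, during the study, and lifts only after treatment failure. The study runs on to the end-of-study visit. On that reading, commercial romiplostim given after a planned stop would presuppose failure in ROM+DEX too, and the asymmetry would largely close. This stands as far as it goes: a reader might infer that the direction of the bias is certain, and 9.i prevents that. It does not dispose of the point, because 9.c allows routine-practice re-treatment once study drug stops and names romiplostim, and 9.f, the section that defines failure, gives no such criterion for ROM+DEX.

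Second, a reader might infer that any re-treated loss of response is a failure in DEX. The DEX-only sentence is narrower: it needs a switch to a TPO-RA. A DEX patient who relapses after one or two cycles and is re-treated with something else is not covered by it.

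Third, the undated DEX rule of below 30 after 3 cycles may already catch many relapses, so the TPO-RA sentence may not be the main source of the excess. That is fair. It changes where the asymmetry sits but does not remove it, since the ROM+DEX rule has no equivalent reach after a planned stop.

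Fourth, the illustration rests on invented shares, and its range is too wide to bound anything. That is accepted; it shows a mechanism and is not an estimate. Steering Committee discussion does not help either: it supplies no criterion for an ordinary relapse in ROM+DEX.

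**Conclusion.** The point holds as a defect in the failure definition. On the 9.f/9.c reading, the compared proportion of treatment failure favours ROM+DEX even when the true courses are identical. On the 9.i reading this may not be so, and the protocol does not say which section governs.

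The size is unknown. The gap of 2.1 to 31.9 points and the 5% to 98% chance of a significant result depend entirely on the assumed shares s and c, on equal true courses, and on the simplifications listed with the inputs.

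The stakes are limited. A reader might infer that the primary result is at risk, but 6mSROT-50 requires the absence of any ITP treatment in both arms, so re-treatment within its 6-month period already fails it whatever 9.f says. Section 11.e labels secondary results exploratory. That label asks for caution but does not correct a definition that differs by arm. Severity is low to moderate.

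**What to change.** - **9.f, common rule:** replace the DEX-only sentence with one rule for both arms. Loss of response after the end of study treatment that leads to new or resumed ITP therapy, including commercial romiplostim or another TPO-RA, is treatment failure. It is dated at the start of that therapy and counted within the same window after treatment cessation in both arms, for example 180 days or 12 months.
- **9.f, arm-specific rules:** limit the 3-cycle rule and the rule of 4 weeks at 10 mcg/kg to the on-treatment response assessment.
- **9.i:** limit the prohibition to the period on study treatment, so that 9.c governs afterwards.

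The cost is protocol wording. Section 9.h already records start dates, and "Concomitant therapies are to be collected from screening through the EOS visit, as applicable". In Table 3 the ITP and rescue medication rows carry no scheduled mark after Month 12, so later re-treatment would come from the concomitant medication record. The downside is that treatment failure will overlap more with loss of response and SROT.

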Once romiplostim or dexamethasone is stopped after 365 days since randomization, patients should be clinically evaluated minimum every 4±1 weeks for 6 months (180 days) and continuation of treatment should be decided on an individual basis by the treating physician. At specified visits outlined in the Study Schedule, patients will undergo physical exams including measurement of vital signs (respiratory rate, body temperature, blood pressure, and pulse rate), height (only at screening visit) and weight, blood counts with absolute and relative differential (neutrophil, lymphocyte and monocyte) blood chemistry profiles (serum creatinine, ALT, AST, GGT, K, Na, LDH), platelet counts, haemoglobin counts as well as review of adverse events and serious adverse events. Measurements of treatment response, health-related quality of life, and other measurements of efficacy per SOC will be collected.

In this study approximately 126 patients will participate. They will be enrolled in 30 study sites from Spain, United Kingdom and Italy.

i. Disease

Primary Immune thrombocytopenia

j. Study outcome measures

Primary outcome measure:

To evaluate the difference between study arms in the proportion of patients achieving 6mSROT-50 at 6 months (180 days) from treatment cessation.

Definition of 6mSROT-50: platelets higher or equal than 50x10⁹/L in the absence of any ITP treatment including any rescue treatment for at least 6 consecutive months (≥180 days) from treatment cessation and without WHO grade 2 or more bleeding.

Secondary outcome measures:

- To evaluate the difference between study arms in the proportion of patients achieving 6mSROT-30 at 6 months (180 days) from treatment cessation.
 - Definition of 6mSROT-30: platelets higher or equal than 30x10⁹/L
 in the absence of any ITP treatment including any rescue treatment
 for at least 6 consecutive months (≥180 days) from treatment
 cessation and without WHO grade 2 or more bleeding.

- To evaluate the difference between study arms in the proportion of patients achieving 12mSROT-50 at 12 months (365 days) from treatment cessation.
 - Definition of 12mSROT-50: platelets higher or equal than 50x10⁹/L
 in the absence of any ITP treatment including any rescue treatment
 for at least 12 consecutive months (≥365 days) from treatment
 cessation and without WHO grade 2 or more bleeding.

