In the DEX arm, if platelet counts are lower than 20x10⁹/L or bleeding symptoms related to thrombocytopenia are present between cycles, rescue therapy with IVIg (maximum dose 2 gr/kg during 1 to 5 days) or low doses of prednisone (0,5 mg/kg/d) could be used. If patients use rescue treatment with prednisone low doses, they should be decreased as soon as possible in a maximum of 8 weeks. It would be considered treatment failure if platelets are lower than 30x10⁹/L after 3 cycles of dexamethasone or rescue medication is needed to get this level of platelets despite the 3 cycles of dexamethasone.

Once romiplostim or dexamethasone is stopped or after 365 days since randomization, patients should be clinically evaluated minimum every 4±1 weeks for 6 months (180 days) and continuation of treatment should be decided on an individual basis by the treating physician. If patient needs treatment again it will be prescribed according to routine clinical practice. If romiplostim is used, it will not be supported by the sponsor.

At specified visits outlined in the Study Schedule, patients will undergo physical exams including measurement of vital signs (respiratory rate, body temperature, blood pressure, and pulse rate), height (only at screening visit) and weight, blood counts with absolute and relative differential (neutrophil, lymphocyte and monocyte)blood chemistry profiles (serum creatinine, ALT, AST, GGT, K, Na, LDH), platelet counts, haemoglobin counts as well as review of adverse events and serious adverse events. Measurements of treatment response, health-related quality of life, and other measurements of efficacy per SOC will be collected.

In this study approximately 126 patients will participate. They will be enrolled in 30 study sites from Spain, United Kingdom and Italy.

b. Primary endpoint

Primary outcome measure:

To evaluate the difference between study arms in the proportion of patients achieving 6mSROT-50 at 6 months (180 days) from treatment cessation.

 Definition of 6mSROT-50: platelets higher or equal than 50x10⁹/L in the absence of any ITP treatment including any rescue treatment for at least 6 consecutive months (≥180 days) from treatment cessation and without WHO grade 2 or more bleeding.

c. Secondary endpoints

Secondary outcome measures:

- To evaluate the difference between study arms in the proportion of patients achieving 6mSROT-30 at 6 months (180 days) from treatment cessation.

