Study time point	Days -28 to -1	Day 1	Weekly visits until Week 7	Week 8	Weekly or biweekly visits until Week 14 ¹¹	Week 16 and week 20	Week 24 (Month 6)	Monthly visits until Month 11	Month 12	Monthly visits until Month 17 ¹²	Month 18 ¹²	Unscheduled visit
			±1 days	±1 days	±1 days	±3 days	±7 days	±3 days	±7 days	±7 days	±7days	
Eligibility criteria	Х	Х										
Informed consent ¹	Х											
Medical history ³	Х											
Demographics ²	Х											
Pregnancy test ⁴	Х											
Randomization		Х										
Vital signs ⁵	Х	Х	Х	Х	X ⁵	Х	Χ	Х	Х	X	Х	X
Physical examination ⁶	Χ	Х	X ⁶	Х	X _e	Х	Х	Х	Х	Х	Х	X
Laboratory tests ⁷	Χ	Х	Х	Х	Х	Х	Х	Х	Х	X	Х	Х
WHO Bleeding score	Х	Χ	Х	Χ	Х	Х	Χ	Х	Х	X	X	X
HRU and loss of productivity8		Χ	X	Χ	X	Χ	Χ	X	Χ	X	Χ	
Quality of life questionnaires:9 SF36, FACIT, ITP PAQ		Χ		Χ			X		Χ		Χ	
ITP-BAT ¹⁰	Х	Χ		Χ	X ¹⁰		Χ		Х		X	
ITP medication		Χ	Х	Х	Х	Х	Χ	Х	X			
Rescue medication		Х	Х	Х	Х	Х	Х	Х	Х			Х
Concomitant medication		Χ	Х	Χ	X	Х	Χ	Х	X	X	Χ	X
AEs/Bleeding event reporting//splenectomy		Х	Х	Х	Х	Х	Х	Х	Х	Х	Х	Х

- 1. Informed consent must be signed and dated prior to any study-related procedure and before any data is recorded in the CRF.
- 2. Demographic data collection including sex, age, and ethnicity.
- 3. Medical history includes all information related to a new diagnosis of ITP and bleeding events history.
- 4. The pregnancy test at screening will be conducted 72 hours before first dose of study treatment.
- 5. Vital signs includes respiratory rate, body temperature, blood pressure, and pulse rate. They must be measured every week until week 8, then every 4 weeks.
- 6. Physical examination will be performed as per standard of care. Physical measurements include height (at screening) and weight (at screening, baseline and from then on every 4 weeks+/- 1 week). There shall be no dose adjustments until changes of 10% or more in weight.
- 7. Complete blood counts with differential, blood chemistry profiles (serum creatinine, ALT, AST, GGT, K, Na, LDH) and platelet counts.
- 8. HRU and loss of productivity shall be measured monthly.
- 9. Quality of life (SF36 v2, FACIT-F and IPT-PAQ) will be evaluated at Day 1, week 8, Month 12 and End of study Visit (visit 12 months after the last dose of study treatment).
- 10. ITP-BAT will be evaluated to screening, Day 1, Week 8, Week 12, Month 6, Month 12 and End of study Visit (visit 12 months after the last dose of study treatment).

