- 11. In the DEX arm, patients will be reviewed every 14 days for 2 months (until Week 16). In the ROM + DEX arm patients will be reviewed weekly if romiplostim dose is changed. If a stable dose of romiplostim is reached or it has been stopped, patient will be reviewed every 14 days for 2 months (until Week 15) (see 9.c Treatment duration and monitoring).
- 12. Once romiplostim or dexamethasone is stopped, patients should be clinically evaluated periodically for 12 months after the treatment stops (see 9.c Treatment duration and monitoring).

Romiplostim arm

Visit number	Visit 0 Screening	Visit 1 Baseline	Visit 2- 8	Visit 9	Visit 10-16	Visit 17-18	Visit 19	Visit 20-24	Visit 25 (End of study treatment Visit, if not ended before)	Visit 26-36 (Periodical clinical evaluation after the end of study medication ¹¹)	Visit 37 (End of study Visit) ¹²	
Study time point	Days -28 to -1	Day 1	Weekly visits until Week 7	Week 8	Weekly or biweekly visits until Week 15 ¹¹	Week 16 and week 20	Week 24 (Month 6)	Monthly visits until Month 11	Month 12	Monthly visits until Month 23 ¹²	Month 24 ¹²	Unschedule d visit
			±1 days	±1 days	±1 days	±3 days	±7 days	±3 days	±7 days	±7 days	±7days	
Eligibility criteria	Х	х										
Informed consent ¹	Х											
Medical history ³	Х											
Demographics ²	Х											
Pregnancy test ⁴	X											
Randomization		Х										
Vital signs⁵	Х	Х	Х	Χ	X ⁵	Х	Χ	Х	Х	Х	X	Х
Physical examination ⁶	Х	Х	X ⁶	Х	X ₆	Х	Χ	Х	Х	Х	Х	Х
Laboratory tests ⁷	Х	Х	Х	Χ	Х	Х	Χ	Χ	Х	X	Х	Х
WHO Bleeding score	Χ	Х	Х	Χ	Х	Х	Χ	Х	Х	Х	X	Х
HRU and loss of productivity8	Х	Х	X	Χ	X	X	Χ	X	X	X	X	
Quality of life questionnaires:9 SF36, FACIT, ITP PAQ		Х		Χ			Χ		X		X	
ITP-BAT ¹⁰	Х	Х		Х	X ¹⁰		Χ		Х		Х	
ITP medication		Х	Х	Χ	Х	Х	Х	Х	Х			
Rescue medication		Х	Х	Х	Х	Х	Х	Х	Х			Х
Concomitant medication		Х	Х	Х	Х	Х	Х	Х	Х	Х	X	Х
AEs/Bleeding event reporting//splenectomy		Х	Х	Х	Х	Х	Х	X	X	Х	Х	Х

- 1. Informed consent must be signed and dated prior to any study-related procedure and before any data is recorded in the CRF.
- 2. Demographic data collection including sex, age, and ethnicity.
- 3. Medical history includes all information related to a new diagnosis of ITP and bleeding events history.
- 4. The pregnancy test at screening will be conducted 72 hours before first dose of study treatment.
- 5. Vital signs includes respiratory rate, body temperature, blood pressure, and pulse rate. They must be measured every week until week 8, then every 4 weeks.

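### Table 3 pins the end-of-study visit to a fixed month (18 in DEX, 24 in ROM+DEX), which does not match the protocol's definition of 12 months after the last dose

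*Protocol*

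**What the plan says.** Table 3 has one schedule per arm.

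- **DEX arm.** Visits 26-36 are "Monthly visits until Month 17". The next column is headed "Visit 37 (End of study Visit" and timed at Month 18, ±7 days.
- **Romiplostim arm.** The same visit numbers are "Monthly visits until Month 23", with the end-of-study visit at Month 24, ±7 days. Visit 25 at Month 12 is labelled "End of study treatment Visit, if not ended before", so early stopping is foreseen, but the Month 24 entry does not move with it.

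The footnotes under both tables define the visit differently. Footnote 10 times ITP-BAT at "Month 12 and End of study Visit (visit 12 months after the last dose of study treatment", and footnote 9 does the same for quality of life. Footnote 12, attached to the Month 17 and 18 cells in DEX and the Month 23 and 24 cells in romiplostim, reads: "Once romiplostim or dexamethasone is stopped, patients should be clinically evaluated periodically for 12 months after the treatment stops". The last-dose definition recurs in the secondary endpoints (sections 1.j and 6.c), the design (6.a) and the analysis text (11.e.i).

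The text on follow-up does not settle the matter:

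- Section 1.h: "Once romiplostim or dexamethasone is stopped after 365 days since randomization, patients should be clinically evaluated", for 6 months.
- Section 6.a starts follow-up at drug stop or after Day 365: "patients should be clinically evaluated minimum every 4±1 weeks for 6 months (180 days".
- Section 9.c uses the same start as 6.a but gives 12 months.
- Section 8.c requires at least 6 months after stopping, in both arms.

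**The concern.** The month label and the definition cannot both hold in the DEX arm, and in the romiplostim arm they agree only for patients treated for the full year. The Study Assessments and Procedures section makes adherence to the schedule mandatory, so a site that obeys the table will see patients at the wrong time from last dose.

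Section 11.e.i compares the arms at this visit on CR, R, GR and TR (proportions) and on SF-36v2, FACIT-F, ITP-PAQ and ITP-BAT (scores). These results would be reported as 12 months after the last dose when time off drug differs between arms, and within the romiplostim arm. After Month 12, Table 3 schedules the questionnaires and ITP-BAT only at the end-of-study visit, so an assessment made at the wrong time has no later replacement.

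**Working it through.** **Inputs.** DEX regimen: 4 days per cycle, one to three cycles, cycle starts 14 to 28 days apart (1.h, 6.a, 9.b). Defined visit: last dose + 365 days. Printed visits: Month 18 and Month 24, ±7 days. One month = 30.44 days.

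**Where Month 18 comes from.** Day 365 + 180 = Day 545, or 545 / 30.44 = 17.9 months. This matches the wording in 1.h (stop after Day 365, then 6 months). It uses both a different start and a different length from the visit definition, and dexamethasone given on schedule cannot stop after Day 365.

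**DEX arm.** Last dose day = 4 + (cycles − 1) × interval. Defined visit = last dose + 365. Days off drug at Month 18 = 545 − last dose. Days late = days off drug − 365.

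| Cycles | Last dose (Day) | Defined visit (Day) | Days off drug at Day 545 | Days late |
|---|---|---|---|---|
| 1 | 4 | 369 | 541 | 176 |
| 2 | 18-32 | 383-397 | 513-527 | 148-162 |
| 3 | 32-60 | 397-425 | 485-513 | 120-148 |

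The defined visit falls at Month 12.1 to 14.0. Month 18 is 485 / 30.44 = 15.9 to 541 / 30.44 = 17.8 months off drug. With Month 18 taken as Day 548 (18 × 30.44), every delay grows by 3 days, to 123-179. For Month 18 to be correct, the last dose would have to fall on Day 545 − 365 = Day 180, which no on-schedule course reaches.

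**Romiplostim arm, full duration.** Last dose Day 365, so the defined visit is Day 730 = Month 24. The table is right here.

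**Romiplostim arm, early taper.** Using the tapering rule in 9.b from the 3 mcg/kg start: 4 weeks at 3, 1 week at 2, 4 weeks at 1, then 4 doses 14 days apart (8 weeks). That is 4 + 1 + 4 + 8 = 17 weeks = Day 119, or 3.9 months. At Month 24 the patient is 24 − 3.9 = 20.1 months off drug. The defined visit would be Day 119 + 365 = Day 484, about Month 15.9.

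**What the data could still give.** Platelet counts and WHO bleeding scores are scheduled monthly after Month 12, so a visit near the defined date exists for CR, R, GR and TR. For questionnaires and ITP-BAT in DEX, the choices are Month 12 or Month 18. At Day 365 a one-cycle patient is 361 days off drug, inside ±7 of the target. A two-cycle patient is at 333-347 days and a three-cycle patient at 305-333, both outside it.

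**The case against.** The definition is stated many times and the month label once per arm, so a careful site or analyst could treat the label as nominal and let the footnote govern. That is a fair account of the intention, but the binding schedule still prints a month, and in DEX no on-schedule patient can satisfy both.

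The impact is limited, and this stands. Section 11.e.i declares the secondary endpoints exploratory. The arms are also compared at Day 180 and Day 365 from randomisation, where time off drug differs by design. Month 12 lies only 4 to 60 days before the defined DEX visit, so assessments fairly near the target exist.

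A reader might infer more than the protocol supports:

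- **That the primary endpoint is compromised because treatment cessation is undefined.** The natural reading is the last study dose: section 8.c speaks of stopping study treatment in both arms, and footnote 12 of treatment stopping. The rival Day 365 reading rests mainly on the 1.h sentence, which lacks the *or* printed in 6.a and 9.c. On the last-dose reading the 180-day DEX window ends by Day 60 + 180 = Day 240 and can be measured.
- **That only the DEX table is wrong.** Correcting DEX alone would leave early romiplostim stoppers up to about 20 months off drug.
- **That the eleven numbers for Visits 26-36 against five DEX months mean visits are missing.** DEX numbering already skips elsewhere, which suggests labels shared with the other table.

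**Conclusion.** The inconsistency is real and lies inside Table 3. The DEX end-of-study visit is printed 120 to 176 days later than the protocol's definition places it, at about 16 to 18 months off drug. The romiplostim Month 24 is correct only for treatment to Day 365 and can be as much as about 20 months off drug. Eight exploratory between-arm comparisons carry a 12-month label that the schedule does not deliver; the quality-of-life and ITP-BAT ones generally cannot be repaired from other scheduled visits.

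The DEX figures assume cycles on schedule, with no delay beyond 28 days. The romiplostim figure assumes the fastest taper from the starting dose; the protocol gives no distribution of stopping times. Neither the direction nor the size of any bias can be derived: longer time off drug allows more relapse, but also more routine treatment after relapse. This should be fixed, but it does not threaten the primary analysis.

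**What to change.** - In both Table 3 schedules, replace the fixed month for Visit 37 with 365 ± 7 days after the last dose of study treatment, and let the monthly visits run up to it.
- Keep Month 18 (DEX) and Month 24 (ROM+DEX) only as labelled additional follow-up, outside the end-of-study comparisons. This avoids shortening observation for endpoints accumulated over the whole study period.
- Make 1.h, 6.a and 9.c agree on 12 months of follow-up after the last dose.

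Cost: text and table edits, with no change to treatment or sample size. One quality-of-life and ITP-BAT assessment is re-timed per patient, except in romiplostim patients treated to Day 365, whose visit stays at Day 730. For one-cycle DEX patients the new visit (Day 369) nearly coincides with Month 12.

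Three tidy-ups could go into the same amendment, though the point does not depend on them: define treatment cessation as the last study dose, renumber the DEX follow-up visits, and reconcile participation duration (24 months in 1.m, 18 months in 4.f).
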